# 8.6.1 Dose Limiting Toxicities

Participants with DLTs as captured on the CRF, including AEs meeting the protocol-defined DLT criteria outside the DLT window will be tabulated using frequency statistics by part and dose level using the All Treated population "as assigned" and "as treated". A listing of DLTs will be provided.

# 8.6.2 Deaths

All deaths during the study within 100 days after the last dose of either study treatment will be summarized for cause of death. All recorded deaths for the All Enrolled population will be listed.

#### 8.6.3 Other Serious Adverse Events

Overall summary of SAEs and treatment-related SAEs by worst CTC grade will be presented by SOC/PT. An SAE listing will be provided for the All Enrolled population.

# 8.6.4 Adverse Events Leading to Discontinuation of Study Therapy

AEs leading to study treatment discontinuation are AEs with action taken = "Drug Withdrawn". Overall summary of AEs leading to discontinuation and treatment-related AEs leading to discontinuation by worst CTC grade will be presented by SOC/PT. An AEs leading to discontinuation listing will be provided.

# 8.6.5 Adverse Events Leading to Dose Modification

AEs leading to dose delay and drug interruption will be summarized. Listings for AEs leading to dose delay and drug interruption will be provided.

#### 8.6.6 Overall Adverse Events

Overall summary of any AEs and treatment-related AEs by worst CTC grade will be presented by SOC/PT. All recorded AEs occurring in the pre-treatment, on-treatment, and post-treatment period will be listed.

### 8.6.7 Select Adverse Events

The select AEs consist of a list of PTs grouped by specific categories (eg, pulmonary events, gastrointestinal events, etc.). Categories of select AEs may include subcategories (eg, adrenal disorders, diabetes, pituitary disorders, and thyroid disorders are subcategories of the endocrine event category).

- For BMS-986277, custom Standard MedDRA Queries (cSMQs) for AE categories and PTs within categories may be defined based on a priori knowledge, new or evolving knowledge from this study, from similar studies (eg, SPICE), and evolving knowledge about oncolytic viruses in general. For Part 1, the BMS-986277, this list, if exists, will be used.
- For nivolumab, AEs that may differ from or are more severe than AEs caused by non-immunotherapies and AEs whose early recognition and management may mitigate severe toxicity are included as select AEs. For Parts 2 and 3, the cSMQs for BMS-986277 will be merged with the nivolumab dictionary.

These select AE lists and the categories are defined by the Sponsor and the lists that is the most current at the time of analysis will be used. Changes may be made to these lists with each new version of MedDRA prior to database lock. The lists that are most current at the time of analysis will be used and included as a listing in each deliverable with select AE analysis.

Overall summary of any select AEs, treatment-related select AEs, serious select AEs, treatment-related serious select AEs, select AEs leading to discontinuation, treatment-related select AEs

leading to discontinuation, by worst CTC grade will be presented by category or subcategory/PT. Select AE definition and an event-level select AE listing will also be provided.

# 8.6.8 Exposure-Adjusted Adverse Events

Analyses that take into account the multiple occurrences of a given AE will be conducted. In order to prepare these analyses, the CRF data will be processed according to standard BMS algorithms  in order to collapse AE records into unique records based on the PT. This data will be presented as the rate per 100 patient-years. These analyses will take into account all on-treatment events (allowing more than 1 event per participant) and the total duration of AE follow-up that is based on exposure to the study medication(s), defined as the first dose of either study treatment to last dose of either study treatment. The patient-years will be computed as the sum over the participants' follow-up expressed in years and is defined as:

- Date of last dose of either study treatment date of first dose of study treatment + 100 + 1 days, for participants who are off study treatment and were followed for at least 100 days after the last dose of either study treatment.
- Last known alive date date of first dose of study medication +1, for participants who are still on treatment or who are off study treatment and were followed less than 100 days after the last dose of either study treatment.

When specified the 95% CI of the rate per 100 person-year of exposure will be derived using normal approximation and variance estimation proposed in Cook and Lawless.

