## **5.2 Number of Participants**

- Part 1 (Monotherapy Dose Escalation - BMS-986277)
  - Initially, 3-6 participants per BMS-986277 monotherapy dose level, for a total of up to 24 participants. Additional participants (up to a total of 12) may be treated at any dose level to further evaluate the safety, PK, or pharmacodynamic profile. Therefore, the total sample size is up to 72.
- Part 2 (Combination Dose Escalation - BMS-986277 and nivolumab)
  - Initially, 3-6 participants per combination dose level. Additional participants (up to a total of 12) may be treated at any dose combination below or at the BLRM-RD for further evaluation of the safety, PK, or pharmacodynamic profile. Therefore, the total sample size is up to 36.
- Part 3 (Combination Expansion)
  - Cohorts 1-2 (BMS-986277 and nivolumab): Up to 40 evaluable participants per cohort. See [Section 10.1](#) for further details on sample size calculation.
  - Cohort 3 (BMS-986277 monotherapy with option for subsequent nivolumab therapy): Up to approximately 12 participants evaluable for pharmacodynamic endpoints will be treated in this cohort. See [Section 10.1](#) for further details on sample size.

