# 8.6 Safety

Analysis of safety will be based on the All Treated population and presented by part, dose level, and overall; tabulations by cohort, indication, and biomarker level may also be performed, as appropriate. Deaths and SAEs will be listed using the All Enrolled population. The treatment groups will be "as treated" as defined in Section 7.2.

Adverse events will be coded according to the most current version of MedDRA at the time of each database lock and the severity will be graded using the NCI CTCAE version 4.03. Treatment-related AEs are those events with relationship to study treatment "Related" as recorded on the CRF. If the relationship to study treatment is missing, the AE will be considered as treatment related.

Listing of AEs will include all enrolled participants, as SAEs and deaths are collected pretreatment. Summaries of AEs will include (1) events occurring from the first dose date to 30 or 100 days (inclusive) after the last dose of either study treatment for Part 1 or Parts 2-3, respectively, for participants who are off study treatment and (2) all events occurring from first dose date for participants who are still on study medication.

Unless otherwise specified, the AE summary tables will be restricted to on-treatment events regardless of the causality. AEs and treatment-related AEs will be tabulated by descending frequency of system organ class (SOC) and descending frequency of preferred term (PT) within each SOC, unless otherwise specified. When reporting AEs by CTC grade, summary tables will be provided based on the event with the worst CTC grade (independent of relationship to study medication). Participants will only be counted (1) once at the PT level, (2) once at the SOC level, and (3) once in the 'Total participant' row at their worst CTC grade, regardless of SOC or PT.

The analysis of laboratory results will be based on the All Treated population with available data. Laboratory results will be categorized according to NCI CTCAE version 4.03 grade. Baseline is defined in Section 7.1.1. Summaries of laboratory results include baseline and (1) post-baseline results up to 100 days (inclusive) after the last dose of either study treatment for participants who are off study treatment and (2) all available post-baseline results for participants who are still on study medication.

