# **Summary**:

The following summary tables will be provided:

- Total number and rate (exposure adjusted, ie, patient-year event rate) of occurrences for all AEs
- For select AEs
  - The number of participants experiencing an AE once or multiple times by part and dose level

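### Where a 95% CI is specified for an exposure-adjusted AE rate, the SAP's normal approximation has no rule for zero or few events and breaks down at dose-level sample sizes

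*SAP*

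**What the plan says.** SAP 8.6.8 (Exposure-Adjusted Adverse Events) defines a recurrent-event rate per 100 patient-years, "allowing more than 1 event per participant". Follow-up runs from first to last dose plus 100 + 1 days for participants followed that long. The interval is conditional: when specified, "the 95% CI of the rate per 100 person-year of exposure will be derived using normal approximation and variance estimation", with an estimator that is cited but not written out. No scale, minimum count or zero-event rule is given.

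The outputs listed under 8.6.8 are "Total number and rate (exposure adjusted, ie, patient-year event rate) of occurrences for all AEs" and, for select AEs, "The number of participants experiencing an AE once or multiple times by part and dose level". Neither names a CI, and only the second, a participant count, is explicitly by dose level.

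The general rule in SAP 8.6 is: "Analysis of safety will be based on the All Treated population and presented by part, dose level, and overall". Protocol 5.2 sets the group sizes: "Initially, 3-6 participants per BMS-986277 monotherapy dose level, for a total of up to 24 participants", rising to 12 at any dose level. SAP 6.2 allows 15 in Part 2, and Protocol 5.2 allows up to 40 evaluable participants in each of Part 3 Cohorts 1 and 2.

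**The concern.** A normal approximation on a rate needs a reasonable number of events and, if the variance is estimated between participants, a reasonable number of participants. A dose level of three may have neither. The section concerns repeated occurrences of a given AE and collapses records by preferred term, so rows with no event or one event are likely if rates are shown at that level.

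Safety is the primary objective of this first-in-human study. A row printed as 0 with limits 0 to 0 tells the reader that the event rate at that dose is known to be exactly zero. A negative lower limit is impossible for a rate.

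**Working it through.** The documents give no event rate or coverage figure for this interval, so there is nothing to reproduce beyond the nominal 95%.

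**Inputs**
- Follow-up per participant: the last planned Part 1 dose is Cycle 2 Day 5, which is study Day 47 (Protocol 7.1.3.1, 42-day Cycle 1). That gives 46 + 100 + 1 = 147 days = 147/365.25 = 0.402 years. Three participants contribute T = 1.207 patient-years.
- Group sizes: 3, 6 and 12 (Protocol 5.2), with 15 and 40 also checked.
- Assumptions: natural scale, equal follow-up, and two candidate variances, because the SAP prints none.

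**Formulas** (D = total events, rate = D/T)
- Normal interval: rate ± 1.96 × SE.
- Robust SE: √Σ(nᵢ − rate × tᵢ)² / T. Poisson SE: √D / T.
- Exact Poisson limits: χ²(0.025; 2D)/(2T) to χ²(0.975; 2D+2)/(2T).

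**Zero events.** Both SEs are 0, so the interval is 0 to 0 at every n. The exact upper limit at n=3 is 3.689/1.207, or 306 per 100 patient-years (n=6: 153; n=12: 76).

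**One event, n=3.** Rate = 1/1.207, or 82.8 per 100 patient-years. The residuals are 2/3, −1/3 and −1/3, with sum of squares 0.667. SE = 0.816/1.207, or 67.6 per 100. Limits: 82.8 ± 132.5, that is −50 to 215. Exact: 2 to 461. In general, one event gives a robust SE of √((n−1)/n)/T, and 1.96 × √((n−1)/n) exceeds 1 for every n of 2 or more. The lower limit is therefore always negative. At n=12 the interval is −18.1 to 59.6.

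**One event in each of three participants.** All residuals are 0, so the robust interval is 248 to 248. Exact: 51 to 726.

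**Two or three events.** With Poisson variance the lower limit is negative whenever D < 1.96² = 3.84, so for 1 to 3 events. With robust variance it depends on the spread. Two events in different participants give +33.1 at n=3, −10.9 at n=6 and −11.0 at n=12. Three in different participants give +24.8 at n=6 and +1.2 at n=12.

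**Coverage.** A zero-event result never covers a positive rate, so coverage cannot exceed P(at least one event). With Poisson counts that is 1 − e^(−0.3) = 26% at 0.3 expected events in the group, and 6% at 0.06. Simulated robust-variance coverage, with ranges spanning Poisson counts and gamma-Poisson counts with dispersion 1:

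| Mean events per participant | n=3 | n=6 | n=12 |
|---|---|---|---|
| 0.1 | 23-24% | 43-45% | 68-70% |
| 1 | 64-71% | 80-85% | 87-91% |
| 10 | 68-73% | 81-87% | 87-91% |

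More events do not rescue the robust form at small n. The Poisson variance reaches about 93-95% at mean 10 without overdispersion, but only about 42-45% with dispersion 1.

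**The case against.** - **The interval is conditional.** A reader might infer that every dose-level rate will carry it. The documents do not say so: it applies only when specified, no listed 8.6.8 output names one, and the dose-level reading comes from the general text of SAP 8.6. If the rate table is a single all-AE total, zero events in a treated dose level is unlikely. This stands. But the sentence fixes the method wherever an interval is produced, and SAP 10 leaves the list of analyses to the Data Presentation Plan.
- **Small groups are partly handled.** Protocol 10.3 allows listings only when data are insufficient, and SAP 8.1 allows groups to be combined. Both are discretionary and neither sets a minimum event count, so they limit the exposure without repairing the method.
- **Scale and variance are not stated.** This stands, and the figures above are conditional on it. The natural scale is the plausible reading, because SAP 8.5 names a log-log transform where one is used. On a log scale negative limits disappear, but zero events becomes undefined, so a rule is still needed.
- **The denominator is debatable.** For Part 1, SAP 7.1.2 counts events to 30 days after the last dose, while 8.6.8 adds 100 days of follow-up. On 46 + 30 + 1 = 77 days the zero-event exact upper limit at n=3 would be about 583, not 306. The two sections need reconciling, but 0 to 0 stays 0 to 0.
- **Nothing is decided on these rates.** Escalation uses DLTs and the Bayesian model with overdose control, and other AE tables and listings sit alongside. This stands and caps the consequence.

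**Conclusion.** The defect holds in conditional form: if an interval is produced for a dose level on the natural scale, the stated method gives 0 to 0 at zero events and a negative lower limit at one event, whatever the event rate. The zero-width interval for three participants with one event each requires a robust variance.

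Two stronger readings are not supported. A single coverage range is not a property of the plan, because the documents give no event rates; the figures of about 23-73% (n=3), 43-87% (n=6) and 68-91% (n=12) rest on the assumed robust variance, equal follow-up and 0.1 to 10 mean events per participant. Nor do few events always give negative limits: under the robust variance that is certain only for one event, under the Poisson variance for one to three. Larger groups fare better; at n=40 with at least 12 expected events, coverage is about 92-95% for Poisson counts.

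The consequence is misleading descriptive precision in safety tables, not a wrong test or dose decision. It is worth correcting before database lock.

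**What to change.** Replace the interval sentence in SAP 8.6.8 with a rule of this kind: when a group has no events, give exact Poisson limits; otherwise give the wider of the exact Poisson limits and a log-scale interval using the participant-level robust variance, multiplied by n/(n−1), with a t quantile on n−1 degrees of freedom. State the variance formula in the SAP.

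Both parts are needed. Exact limits alone fall to about 45-60% coverage with 5 to 10 events per participant and dispersion 1, while the robust part alone has zero width when every participant has the same count. In simulation (n from 3 to 40, mean 0.1 to 10, dispersion 0 to 1, equal follow-up) the combined interval covered about 93% or more.

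The cost is SAP wording and a few lines of code, with no new data. The intervals become wide and conservative at n=3. With one event among three, the relative SE is √(0.667 × 3/2) = 1 and the t quantile is 4.303, so the limits are 82.8 divided and multiplied by e^4.303 = 73.9, about 1 to 6,120 per 100 patient-years. If the team finds that unhelpful, it can state a minimum group size below which only the event count and patient-years are shown.

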# **Summary**:

The following summary tables will be provided:

- Total number and rate (exposure adjusted, ie, patient-year event rate) of occurrences for all AEs
- For select AEs
  - The number of participants experiencing an AE once or multiple times by part and dose level

### Listing:

• Unique instances of all AEs, ie, after duplicates have been eliminated and overlapping and contiguous occurrences of the same event (ie, same PT) have been collapsed.

### 8.6.9 Immune-Mediated Adverse Events

In order to further characterize AEs of special clinical interest, analysis of immune-mediated AEs (IMAEs) will be conducted. Immune-mediated AEs are specific events (or groups of PTs describing specific events) that include pneumonitis, diarrhea/colitis, hepatitis, nephritis/renal dysfunction, rash, endocrine (adrenal insufficiency, hypothyroidism/thyroiditis, hyperthyroidism, diabetes mellitus, and hypophysitis), and other specific events, considered as potential immune-mediated events by investigator, that meet the definition summarized below:

- those occurring within 30 or 100 days of the last dose for Part 1 or Parts 2-3, respectively,
- regardless of causality,

- treated with immune-modulating medication (of note, endocrine adverse events such as adrenal insufficiency, hypothyroidism/thyroiditis, hyperthyroidism, diabetes mellitus, and hypophysitis are considered IMAEs regardless of immune-modulating medication use, since endocrine drug reactions are often managed without immune-modulating medication).
- with no clear alternate etiology based on investigator assessment, or with an immune-mediated component

The list of MedDRA preferred terms used to identify Immune-Mediated adverse events is revisited quarterly and updated accordingly. The preferred terms used for the selection at the time of the database lock by categories will be provided. IMAEs will be summarized for Parts 2 and 3 only for each immune mediated category/PT. A by-participant listing of IMAEs will be provided. A listing of AEs considered as Immune-Mediated Events per Investigator as recorded on the CRF but not Qualified for Immune-Mediated AE Definition will also be provided.

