#### **7.4.5 Management of Drug-related Infusion Reactions**

BMS-986277 has the potential to induce hypersensitivity reactions following administration. There is potential risk of cytokine release exhibited with enadenotucirev coupled with potential immune activation from transgenes. These events will be mitigated by an up to 12 hour post infusion observation, laboratory measurements for cytokine release monitoring, staggered dosing of initial participants in each cohort of monotherapy treatment (Part 1) and combination treatment (Part 2) to have no more than 1 patient at a time dosed, and a starting dose selected that is 100 $\times$  below the enadenotucirev RP2D. Refer to [Appendix 10](#) for the treatment algorithm for BMS-986277-associated infusion reactions.

Since nivolumab contains only human immunoglobulin protein sequences, it is unlikely to be immunogenic and induce infusion or hypersensitivity reactions. However, if such a reaction were to occur, it might manifest with fever, chills, rigors, headache, rash, pruritus, arthralgia, hypotension, hypertension, bronchospasm, or other allergic-like reactions. All Grade 3 or 4 infusion reactions should be reported within 24 hours to the study Medical Monitor (or designee) and reported as an SAE if it meets the criteria. Infusion reactions should be graded according to NCI CTCAE (Version 4.03) guidelines.

Treatment recommendations for nivolumab-associated infusion reactions are provided below and may be modified based on local treatment standards and guidelines, as appropriate:

**For Grade 1 symptoms** (mild reaction; infusion interruption not indicated; intervention not indicated):

- Remain at bedside and monitor participant until recovery from symptoms. The following prophylactic premedications are recommended for future infusions: diphenhydramine 50 mg IV (or equivalent) and/or acetaminophen/paracetamol 325 to 1000 mg at least 30 minutes before additional nivolumab administrations.

[figure not shown]
**For Grade 2 symptoms:** (moderate reaction required therapy or infusion interruption but responds promptly to symptomatic treatment (eg, antihistamines, non-steroidal anti-inflammatory drugs, narcotics, corticosteroids, bronchodilators, IV fluids); prophylactic medications indicated for  $\leq 24$  hours):

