### **Follow-up of AEs and SAEs**

If only limited information is initially available, follow-up reports are required. (Note: Follow-up SAE reports must include the same investigator term(s) initially reported.)

If an ongoing SAE changes in its intensity or relationship to study treatment or if new information becomes available, the SAE report must be updated and submitted within 24 hours to BMS (or designee) using the same procedure used for transmitting the initial SAE report.

All SAEs must be followed to resolution or stabilization.

Every adverse event must be assessed by the investigator with regard to whether it is considered immune-mediated. For events which are potentially immune-mediated, additional information will be collected on the participant's case report form.

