#### 5.1.1 Adverse Events

- Incidence rate of adverse events (AEs), serious adverse events (SAEs), AEs meeting the protocol-defined DLT criteria (Protocol Section 7.4.1), AEs leading to discontinuation, and AEs resulting in death
  - DLTs are identified as recorded on the case report form (CRF).
  - All non-serious AEs will be assessed from the start of dosing.
  - All SAEs and deaths will be assessed from the date of the participant's written informed consent.
  - All AEs (serious and non-serious), and deaths will be assessed up to 30 days after the last dose of BMS-986277 for participants enrolled in Part 1 or 100 days after the last dose of any study drug for participants enrolled in Parts 2 and 3.
  - Drug-related AEs are those events with relationship to study drug "Related", as recorded on the CRF. If the relationship to study drug is missing, the AE will be considered as drugrelated.
  - Serious adverse events consist of AEs deemed serious by the Investigator and flagged accordingly in the CRF and clinical database.
  - Adverse events leading to study drug discontinuation are AEs with action taken = "Drug was discontinued".
  - AEs belonging to select AE categories will be assessed using the categorizations which are current at the time of database lock. An accompanying listing will be provided to define the categorizations at each analysis.

- ♦ The select AE categories from the CA209 dictionary will be used, as well as any additional categories and/or AEs within a category that may be particularly relevant or of interest for BMS-986277.
- Immune-mediated AEs may also be summarized if warranted based on sufficient data, relevance, interest, etc.
- AEs will be coded using the most current version of the Medical Dictionary for Regulatory Activities (MedDRA) at the time of each database lock
- AEs will be graded for severity according to the National Cancer Institute (NCI) Common Terminology Criteria for Adverse Events (CTCAE) version 4.03.

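### The SAP defines and lists immune-mediated adverse events in Part 1 but tabulates them by category only for Parts 2 and 3, contrary to its own Section 5.1.1

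*SAP*

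**What the plan says.** SAP 8.6.9 defines an IMAE by timing, treatment and cause. The timing rule covers every part: "those occurring within 30 or 100 days of the last dose for Part 1 or Parts 2-3, respectively". The section promises a listing with no limit by part ("A by-participant listing of IMAEs will be provided"), and a second listing of events that the investigator called immune-mediated but that miss the definition. The table is limited: "IMAEs will be summarized for Parts 2 and 3 only for each immune mediated category/PT". No reason is given.

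SAP 5.1.1 reads differently. On IMAEs it says: "Immune-mediated AEs may also be summarized if warranted based on sufficient data, relevance, interest, etc". On select AEs it says: "The select AE categories from the CA209 dictionary will be used", with further categories added where relevant to BMS-986277. Neither statement is limited by part. SAP 8.6.7 then separates the parts. Parts 2 and 3 use the nivolumab dictionary merged with any BMS-986277 queries, and for Part 1 the text is "For Part 1, the BMS-986277, this list, if exists, will be used".

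On the protocol side, the first primary objective (Table 4-1) covers safety of BMS-986277 alone as well as in combination. Appendix 3 requires the classification for all events: "Every adverse event must be assessed by the investigator with regard to whether it is considered immune-mediated". Section 7.4.5 says of the virus: "There is potential risk of cytokine release exhibited with enadenotucirev coupled with potential immune activation from transgenes".

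**The concern.** Part 1 gives BMS-986277 without nivolumab, and in the design that the SAP describes it is the only part that does. The documents expect the virus to have immune effects of its own. Besides Section 7.4.5, Appendix 9 Section 1.2 justifies a weakly informative prior by possible extra toxicity from T-cell activation. The Document History entry for Revised Protocol 06 says that the Appendix 5 algorithms apply to IMAEs mediated by BMS-986277 as well as by nivolumab.

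As written, Part 1 events can qualify as IMAEs, be derived and be listed, and still not appear in a category table. If no BMS-986277 select-AE list is drawn up, SAP 8.6.7 gives Part 1 no select-AE category table either. The report would then describe the immune toxicity of the virus alone only through listings, individual preferred terms and a few organ-specific summaries, although the classification data are already on the CRF.

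**Working it through.** The point concerns the scope of a table, so there is no planned figure to reproduce. The texts are set side by side first.

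| SAP text | Part 1 | Parts 2 and 3 |
|---|---|---|
| 5.1.1, IMAE summaries | allowed if warranted | allowed if warranted |
| 5.1.1, CA209 select-AE categories | used | used |
| 8.6.7, select-AE list | BMS-986277 list, if there is one | nivolumab dictionary merged with BMS-986277 list |
| 8.6.9, IMAE window after last dose | 30 days | 100 days |
| 8.6.9, IMAE listings | yes | yes |
| 8.6.9, IMAE category/PT table | no | yes |

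Two conflicts follow. SAP 8.6.9 turns an option open to all parts in 5.1.1 into a fixed exclusion of Part 1. SAP 8.6.7 makes conditional for Part 1 what 5.1.1 states outright.

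Next, what Part 1 does receive:
- AE tables by SOC and PT at worst grade, split by part and dose level (SAP 8.6, 8.6.6).
- Hepatic and thyroid laboratory summaries (SAP 8.6.10.1, 8.6.10.2).
- Creatinine, and frequencies for renal function, bladder hemorrhage and cytokine release syndrome (SAP 8.6.12).
- Both IMAE listings (SAP 8.6.9).

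SOC/PT tables do not pool related preferred terms into one clinical category. They also do not apply the two IMAE filters, namely immune-modulating treatment (waived for endocrine events) and no other evident cause or an immune component. The laboratory summaries cover only some of the IMAE categories. The clearest remaining gaps are pneumonitis, diarrhea/colitis, rash and non-thyroid endocrine events.

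Last, would a Part 1 table probably be empty? The documents give no Part 1 IMAE rate, so category rates p of 5%, 10% and 20% are assumed. SAP 6.1 puts Part 1 at about 24 treated, with no more than about 18 DLT-evaluable expected. Protocol 5.2 plans 3-6 per dose level initially. The chance of at least one event is 1 − (1 − p)^n:

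| n | p = 5% | p = 10% | p = 20% |
|---|---|---|---|
| 24 | 1 − 0.95^24 = 71% | 1 − 0.90^24 = 92% | 1 − 0.80^24 = 99.5% |
| 18 | 60% | 85% | 98% |
| 6 | 26% | 47% | 74% |
| 3 | 14% | 27% | 49% |

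If no event is seen, the two-sided 95% exact upper limit is 1 − 0.025^(1/n). That is 14.2% for n = 24, 46% for n = 6 and 71% for n = 3. Pooled over doses, the table would say something useful whether or not events occur. By single dose level it would be imprecise. The pooled figure in turn averages over doses that span a factor of 100 (3 × 10^10 to 3 × 10^12 vp).

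**The case against.** Much of the case on the other side stands.

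- A reader might infer that Part 1 has no tabulated immune toxicity at all. The documents do not support that. The SOC/PT tables, the hepatic, thyroid and renal summaries and the cytokine release frequency all cover Part 1, and IMAEs can be counted by hand from the listing.
- A reader might infer that a Part 1 table would show what the virus adds to nivolumab. It would not. That needs a nivolumab-alone arm, which the trial lacks. Comparison of Part 1 with Part 2 is also blurred by the 30- and 100-day windows, different Cycle 1 schedules, and up to 26 nivolumab cycles in Part 2.
- The 13% for nivolumab at 3 mg/kg in Appendix 9 Table 4 (150/1146) counts all treatment-related Grade 3-4 events. It is not an IMAE rate and does not measure confounding here.
- A reader might infer that this sentence leaves out the monotherapy participants of Cohort 3. Cohort 3 belongs to Part 3. It is absent because SAP version 1.0 follows the protocol only up to Revised Protocol 03 and describes two expansion cohorts.
- IMAE tables are not a named primary endpoint in Table 4-1 or protocol 10.3.2. Section 7.4.5 concerns infusion reactions, and Appendix 9 Section 1.2 concerns a DLT prior.
- SAP 1 allows additional analyses, and SAP 8.1 leaves grouping to the data presentation plan.

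These points narrow the concern but do not answer it. None of the retained tables gives pooled, filtered IMAE categories. A general allowance for extra analyses does not settle an explicit exclusion in the section that governs this table.

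**Conclusion.** The point holds as a limited reporting gap together with an internal inconsistency. SAP 8.6.9 excludes Part 1 from the IMAE category table without giving a reason, and it conflicts with SAP 5.1.1, as does the conditional list in 8.6.7. No data are lost, and part of the immune profile is tabulated elsewhere. What is missing is a category-level description of IMAEs on BMS-986277 without nivolumab, in a trial whose primary objective includes safety of the agent alone.

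The size is modest. With about 24 participants and assumed category rates of 5% to 20%, a pooled Part 1 table would show at least one event with probability 71% to 99.5%. The rates are assumptions, and 24 is the SAP's own maximum; the current protocol allows up to 72 in Part 1. The table would describe events on the virus alone and would not by itself isolate its contribution to the combination. The SAP should be corrected before database lock.

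**What to change.** In SAP 8.6.9, replace the restriction to Parts 2 and 3 with a summary for all parts, by part and dose level and pooled across Part 1 dose levels. In SAP 8.6.7, apply the CA209 select-AE categories to Part 1, together with any BMS-986277 list, so that it agrees with 5.1.1. When the SAP is brought up to the current protocol, show Cohort 3 events with onset before the first nivolumab dose separately from combination events. That update should also reconcile the SAP's 30-day Part 1 window with the 60-day AE collection for monotherapy in protocol Table 2-6.

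The first two changes are a sentence each and use data already collected. The cost is a few more tables, some of which may be sparse by dose level. The Cohort 3 display belongs to a wider SAP update that is needed anyway.
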